## 5.2.2. Analyses for Continuous Endpoints

### 5.2.2.1. Geometric Means

The GBS6 serotype-specific IgG and OPA will be summarized by geometric means (GMCs or GMTs) and the associated 2-sided 95% CIs by vaccine group. The GMCs (GMTs) will be calculated as the mean of the logarithmically transformed assay results and back transformed to its original units. The 2-sided 95% CIs will be constructed by back transformation of the CIs for the mean of the logarithmically transformed assay results using Student's t distribution.

### 5.2.2.2. Geometric Mean Fold Rises

The fold rises in GBS6 serotype-specific antibody levels from before vaccination (Day 1) to each selected postvaccination time point for participants will be summarized, by vaccine group, via geometric means and associated 2-sided 95% CIs. The GMFRs are calculated as the mean of the difference of logarithmically transformed antibody levels after and before vaccination time points and back transformed to the original units. The associated 2-sided 95% CIs are also computed by back transformation of the CIs using Student's t distribution for the mean difference of measures on the logarithmically transformed assay results.

### 5.2.2.3. Reverse Cumulative Distribution Curves

Empirical reverse cumulative distribution curves (RCDCs) will be presented graphically by plotting the proportion of participants with the GBS6 serotype-specific antibody level equal to or exceeding the specified antibody level vs indicated antibody level for each serotype separately, by vaccine group, and at 1 month after vaccination for serotype-specific IgG concentration and OPA titers.

## 5.3. Methods to Manage Missing Data

### 5.3.1. Safety Data

Standard algorithms on handling missing AE dates and missing AE severity will be applied as described in the safety rulebook.

### 5.3.2. Reactogenicity Data

For derived variables based on reactogenicity data, if any day of the 14-day e-diary is available, the "any day (Days 1-14)" data will be considered as nonmissing.

The reactogenicity data are collected through e-diary, which does not allow participants to skip the question. Therefore, for a specific day, as long as the e-diary data are transferred for that day, all of the reactogenicity data for the participant on that day will be considered as nonmissing. No missing reactogenicity data will be imputed other than what is described in [Section 3.5.1](#).

### 5.3.3. Immunogenicity Data

Values for sera that are insufficient sera (QNS), indeterminate results, or recorded as “not done” will be set to “missing.” No imputation will be done for these missing values.

In the first-in-human (FIH) study (C1091001), the LLOQ values in  $\mu\text{g/mL}$  for each serotype of GBS IgG are set as follows: Ia, 0.008; Ib, 0.011; II, 0.009; III, 0.010; IV, 0.005; V, 0.075.

In both FIH and C1091007 studies, the LLOQ values in titer for each serotype of GBS OPA are set as follows: Ia, 126; Ib, 150; II, 363; III, 130; IV, 224; V, 125.

In the C1091007 study, the LLOQ values in  $\mu\text{g/mL}$  for each serotype of GBS IgG are set as follows: Ia, 0.004; Ib, 0.010; II, 0.015; III, 0.012; IV, 0.006; V, 0.043.

The GBS6 IgG and OPA levels above LLOQ are considered accurate and their quantitated values will be reported. Values below the LLOQ or denoted as below the limit of quantitation (BLQ) will be set to  $0.5 \times \text{LLOQ}$  for all analyses.

LLOQ values for the GBS IgG1 and IgM will be updated when they become available.

## 6. ANALYSES AND SUMMARIES

### 6.1. Primary Endpoints

#### 6.1.1. Prompted Local Reactions (Redness, Swelling, and Pain at the Injection Site) Within 14 Days After Vaccination

- Analysis set: Safety ([Section 4](#)).
- Analysis time points: Days 1 through 14. Refer to [Section 3.5.1.1](#) for maximum severity.
- Analysis methodology: Descriptive summary statistics.
- Supporting objective: Primary safety objective.
- Intercurrent events and missing data: For participants who discontinue, all collected data will be included; intermediate missing values will not be imputed.
- For each group, the numerator (n) and denominator (N) used for the calculation of proportion, proportion, and associated 2-sided exact 95% CI will be presented, by vaccine group, for the following variables:

- Presence or absence of each local reaction on each day (Days 1-14) after vaccination.
- Presence or absence of each local reaction on “any day (Days 1-14)” after vaccination.
- Presence or absence of any local reaction on “any day (Days 1-14)” after vaccination.
- Maximum severity of each local reaction on “any day (Days 1-14)” after vaccination.
- For each group, the n, mean, median, minimum, and maximum will be presented by vaccine group for the following variables:
  - Duration of each local reaction after vaccination.
  - Onset day of each local reaction after vaccination.
  - Onset day of any local reaction after vaccination.

**Figures:** None

#### **6.1.2. Prompted Systemic Events (Fever, Nausea/Vomiting, Diarrhea, Headache, Fatigue, Muscle Pain, and Joint Pain) Within 14 Days After Vaccination**

- Analysis population: Safety ([Section 4](#)).
- Analysis time points: Days 1 through 14.
- Analysis methodology: Descriptive summary statistics.
- Supporting objective: Primary safety objective.
- Intercurrent events and missing data: For participants who discontinue, all collected data will be included; intermediate missing values will not be imputed.
- For each group, the numerator (n) and denominator (N) used for the calculation of proportion, proportion, and associated 2-sided exact 95% CI will be presented by vaccine group for the following variables:
  - Presence or absence of systemic event on each day (Days 1-14) after vaccination.
  - Presence or absence of each systemic event on “any day (Days 1-14)” after vaccination.
  - Presence or absence of any systemic event on “any day (Days 1-14)” after vaccination.
  - Maximum severity of each systemic event on “any day (Days 1-14)” after vaccination.

- For each group, the n, mean, median, minimum, and maximum will be presented by vaccine group for the following variables:
  - Duration of each systemic event after vaccination.
  - Onset day of each systemic event after vaccination.
  - Onset day of any systemic event after vaccination.

### 6.1.3. AEs Through 1 Month After Vaccination

- Analysis population: Safety ([Section 4](#)).
- Analysis time points: Day 1 through 1 month after vaccination.
- Analysis methodology: Descriptive summary statistics.
- Supporting objective: Primary safety objective.
- Intercurrent events and missing data: For participants who discontinue, all collected data will be included; missing AE dates will be imputed as described in the safety rulebook.
- For each group, the number of participants with AEs within 1 month (30 days) (n), proportion, and associated 2-sided exact 95% CI will be presented for any AE, each system organ class (SOC), and each PT within each SOC, by vaccine group. For AEs classified as Tier 2, the number of participants with AEs (n), proportion, and associated 2-sided exact 95% CI will be presented for each vaccine group.

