#### **8.1.2. Visit 2 – 1-Month Follow-up Visit (28-38 Days After Visit 1)**

- Ensure that the participant continues to be eligible for the study, meets none of the participant withdrawal criteria as described in [Section 7](#), and meets none of the blood draw temporary delay criteria as described in [Section 5.2.1.2](#).
- Verify the participant's understanding of and compliance with the protocol requirements for contraception.
- Collect a blood sample of approximately 50 mL for immunogenicity assessments. Alternatively, for participants who have consented to participate, collect approximately 150 mL of blood.
- Review the participant's e-diary data and collect the e-diary. Collect stop dates of any e-diary events ongoing on the last day that the e-diary was completed and record stop dates in the CRF.
- Record nonstudy vaccinations and concomitant medications as described in [Section 6.5.3](#).
- Record AEs as described in [Section 8.5](#).
- Complete the participant's source documents.
- The investigator or an authorized designee completes the CRF.

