#### **8.5.1. Time Period and Frequency for Collecting AE and SAE Information**

The time period for actively eliciting and collecting AEs and SAEs (“active collection period”) for each participant begins from the time the participant provides informed consent, which is obtained before the participant’s participation in the study (ie, before undergoing any study-related procedure and/or receiving investigational product), through and including Visit 2 (1 month after vaccination) for AEs and through and including Visit 3 for MAEs and SAEs.

AEs that begin before the start of study intervention but after obtaining informed consent will be recorded on the Medical History/Current Medical Conditions section of the CRF, not the AE section.

Follow-up by the investigator continues throughout and after the active collection period and until the event or its sequelae resolve or stabilize at a level acceptable to the investigator, and Pfizer concurs with that assessment.

Investigators are not obligated to actively seek AEs or SAEs after conclusion of the study participation. However, if the investigator learns of any SAE, including a death, at any time after a participant has completed or withdrawn early from the study, and he/she considers the event to be reasonably related to the study intervention or study participation, the investigator must promptly notify the sponsor.

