### **9.1. Estimands and Statistical Hypotheses**

#### **9.1.1. Estimands**

##### **Primary (Safety):**

In participants receiving at least 1 dose of the investigational product:

- The proportion of participants reporting prompted local reactions within 14 days following investigational product administration.
- The proportion of participants reporting prompted systemic events within 14 days following investigational product administration.
- The proportion of participants reporting AEs through 1 month following investigational product administration.
- The proportion of participants reporting MAEs and SAEs through 6 months following investigational product administration.

Missing e-diary data will not be imputed; missing AE dates and missing AE severity will be handled according to Pfizer safety rules.

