## 2. INTRODUCTION

This statistical analysis plan (SAP) provides the detailed methodology for summary and statistical analyses of the data collected in Study C1091007. This SAP Version 3 is based on the final protocol dated 07 Nov 2019. A brief description of the study design and the study objectives are given below. Subsequent sections describe analysis populations and give the definitions of the safety and immunogenicity endpoints followed by details of statistical reporting. A list of tables, listings, and figures, mock-up tables, listings, and figures, and programming rules are prepared separately based on the methods described in this document. This document may modify the plans outlined in the protocol; however, any major modifications of the primary endpoint definition or its analysis will also be reflected in a protocol amendment.

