## 2.1.3. Primary Estimands

In participants receiving 1 dose of investigational product:

- The proportion of participants reporting prompted local reactions within 14 days following investigational product administration.

This estimand includes the following 4 attributes:

- Population: All participants who receive 1 dose of the investigational product and have safety data reported after receiving the investigational product.
- Variable: Presence/absence of prespecified local reactions within 14 days after vaccination.
- Intercurrent event(s): For participants who discontinue, all collected data will be included; missing data will not be imputed.
- Population-level summary: Proportion of participants reporting local reactions in each vaccine group.

The dose/formulation levels (hereafter referred to as vaccine groups) in this study are defined as below:

1. GBS6 (20 µg)/aluminum phosphate (AlPO4), which is equivalent to 120 µg per 0.5-mL dose with AlPO4.
  2. GBS6 (20 µg)/no AlPO4, which is equivalent to 120 µg per 0.5-mL dose (no AlPO4).
- The proportion of participants reporting prompted systemic events within 14 days following investigational product administration.

This estimand includes the following 4 attributes:

- Population: All participants who receive 1 dose of the investigational product and have safety data reported after receiving the investigational product.
- Variable: Presence/absence of prespecified systemic events within 14 days after vaccination.
- Intercurrent event(s): For participants who discontinue, all collected data will be included; missing data will not be imputed.
- Population-level summary: Proportion of participants reporting systemic events in each vaccine group.
- The proportion of participants reporting adverse events (AEs) through 1 month following investigational product administration.

This estimand includes the following 4 attributes:

- Population: All participants who receive 1 dose of the investigational product and have safety data reported after receiving the investigational product.
- Variable: Presence of AEs within 1 month after vaccination.
- Intercurrent event(s): For participants who discontinue, all collected data will be included; missing AE dates will be imputed as described in the safety rulebook.
- Population-level summary: Proportion of participants reporting AEs through 1 month after vaccination in each vaccine group.

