### 3.5.2. Adverse Events

All AEs, including nonserious AEs and SAEs, are collected on the CRF and will be categorized according to the current version (at the time of reporting) of the Medical Dictionary for Regulatory Activities (MedDRA). The time period for actively eliciting and collecting AEs and SAEs (“active collection period”) for each participant begins from the time the participant provides informed consent, which is obtained before participation in the study (ie, before undergoing any study-related procedure and/or receiving investigational product), through and including Visit 2 (1 month after vaccination) for AEs and through and

including Visit 3 for MAEs and SAEs. AEs that begin before the start of study intervention but after obtaining informed consent will be recorded on the Medical History/Current Medical Conditions section of the CRF, not the AE section. Immediate AEs, defined as AEs occurring within the first 30 minutes after investigational product administration, will be assessed and documented in the AE CRF. The time of onset will be recorded for any AEs that occur on the same day as investigational product administration.

An MAE is defined as a nonserious AE that results in an evaluation at a medical facility.

If an event is not an AE, then it cannot be an SAE even if serious conditions are met (eg, hospitalization for signs/symptoms of the disease under study, death due to progression of disease).

AEs and SAEs will be captured and reported in accordance with Section 10.3.5 of the protocol.

A 3-tier approach will be used to summarize AEs. Under this approach, AEs are classified into 1 of 3 tiers. Different analyses will be performed for different tiers (see [Section 6.6.1](#)).

Tier 1 events: These are prespecified events of clinical importance and are maintained in a list in the product's Safety Review Plan. There are no preidentified Tier 1 events for this study.

Tier 2 events: These are events that are not Tier 1 but are "common." A MedDRA preferred term (PT) is defined as a Tier 2 event if there are 4 or more participants in any vaccine group.

Tier 3 events: These are events that are neither Tier 1 nor Tier 2 events.

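### Does counting primary AEs within 30 days, when AEs are collected through Visit 2 (28 to 38 days), leave a gap that needs a change?

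*SAP*

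**What the plan says.** The third primary estimand in Protocol 9.1.1 is "The proportion of participants reporting AEs through 1 month following investigational product administration", with no day count. SAP 2.1.3 gives the variable as "Presence of AEs within 1 month after vaccination", also without one. The only place that turns the month into days is SAP 6.1.3, which counts "the number of participants with AEs within 1 month (30 days" and gives n, the proportion and an exact 95% CI for any AE, each SOC and each PT.

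Collection follows the visit. Protocol 8.5.1 runs active collection "through and including Visit 2 (1 month after vaccination) for AEs and through and including Visit 3 for MAEs and SAEs", and SAP 3.5.2 repeats this ("through and including Visit 2 (1 month after vaccination) for AEs"). Protocol 8.1.2 places that visit "28-38 Days After Visit 1".

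Three other parts of the plan bear on AEs after 30 days:

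- SAP 6.1.4 tabulates MAEs and SAEs through 6 months.
- SAP 6.6.1 promises proportions for Tier 2 and Tier 3 events, an overall AE summary, and a listing of participants with any AE. It sets no window for any of these.
- SAP 5.2.1.1 and Protocol 9.4.2 promise AE proportions with Clopper-Pearson intervals, again with no window.

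**The concern.** One month appears to mean two things: 30 days in the primary table, and the Visit 2 date in collection. The 30-day proportion can only equal or fall below the proportion through Visit 2. A reader who sees one figure cannot tell how far apart they are.

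The events at issue are nonserious AEs without medical attendance that start after 30 days and by Visit 2. They are collected, but no section explicitly gives them a rate table. The Tier 2 rule, "Tier 2 event if there are 4 or more participants in any vaccine group", has no window either, so whether a term qualifies could depend on the choice. Nor is the 30-day window fully observed for everyone: under Protocol 8.5.1, a participant seen at 28 or 29 days stops active AE collection before day 30.

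Safety is the primary objective, so an unclear window on one of four primary estimands deserves a check.

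**Working it through.** The plan gives no AE rate or expected count to reproduce, so the check is day arithmetic, then an illustration of size, then a reading of what the other sections cover.

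**Days at issue.** Inputs: Visit 2 at 28 to 38 days (Protocol 8.1.2) and a cut-off of 30 days (SAP 6.1.3).

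- Longest gap with an in-window visit: 38 − 30 = 8 days. If 30 days meant study Day 30, with vaccination as Day 1, the latest visit would be Day 39 and the gap 9 days.
- Assume visits are spread evenly over the 11 permitted days. Then 8/11 = 73% of visits fall after 30 days and 2/11 = 18% fall before.
- Mean days collected beyond 30: (1 + 2 + … + 8)/11 = 36/11 = 3.3, out of a mean of 33, or 9.9%.

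**Effect on the proportion.** Assumptions: the proportion through Visit 2 is 10% or 20%, and all 297 eligible completers enrol and split evenly, 297/2 ≈ 148 per group. The probability of an AE by day d is 1 − exp(−H(d)). H(d) = h·d for a constant hazard, or h·[3·min(d, 14) + max(0, d − 14)] for a hazard three times higher in the first 14 days. Solve for h so that the average over d = 28, …, 38 equals the assumed proportion, then recompute with d replaced by min(d, 30).

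| Hazard | Through Visit 2 | Within 30 days | Difference (points) | Participants of 148 |
|---|---|---|---|---|
| Constant | 10% | 9.06% | 0.94 | 1.39 |
| Constant | 20% | 18.23% | 1.77 | 2.63 |
| 3 times higher, first 14 days | 10% | 9.49% | 0.51 | 0.75 |
| 3 times higher, first 14 days | 20% | 19.04% | 0.96 | 1.42 |

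Sensitivity to visit timing: the difference is 0 if every Visit 2 is by 30 days, 0.04 to 0.15 points if visits are spread evenly over 28 to 31 days, and 1.16 to 3.85 points if every visit is at 38 days.

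**Part not covered by SAP 6.1.4.** Assume 25% to 50% of the participants lost from the 30-day count have a late MAE or SAE. The share left is 50% to 75%:

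- lowest: 0.51 × 0.50 ≈ 0.25 points (0.75 × 0.50 ≈ 0.4 participants);
- highest: 1.77 × 0.75 ≈ 1.33 points (2.63 × 0.75 ≈ 2.0 participants).

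**Scale.** The Clopper-Pearson 95% interval for 30/148 (20.3%) is 14.1% to 27.7%, about 13.6 points wide.

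**Coverage.** SAP 3.5.2 names no Tier 1 events, so every AE is Tier 2 or Tier 3. SAP 6.6.1 promises proportions for both tiers without a 30-day limit. On a plain reading, those summaries take every AE collected, including days 31 to 38. Only the SOC and PT table in SAP 6.1.3 is limited to 30 days.

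**The case for a change.** The best case for a change is that silence is not assurance. SAP 6.6.1, SAP 5.2.1.1 and Protocol 9.4.2 set no 30-day limit, but they do not say that they run through Visit 2. Thirty days is the only window stated for AE rates, and a programmer might carry it over. SAP 2 says "programming rules are prepared separately based on the methods described in this document", so the separate rules cannot be counted on to supply what this text omits. A second table through Visit 2 would use data already collected and would show both figures.

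It stands that the window of the tier summaries is unstated. The rest is weaker:

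- The primary quantity is identified. SAP 6.1.3 sits under the primary endpoints, names the primary safety objective as what it supports, and says 30 days. Collecting for somewhat longer than the analysis window is not a contradiction.
- The extra table has its own fault: follow-up would vary from 28 to 38 days with scheduling, whereas the 30-day count uses one cut-off for all.
- Carrying the 30-day window into the Tier 2 rule and SAP 6.6.1 for consistency could do harm. Those are the summaries where late AEs can now appear.
- Making Visit 2 the primary window might count as a major change to a primary analysis, which under Protocol 9 and SAP 2 would also need a protocol amendment.
- The point about visits at 28 or 29 days is less firm than it looks. The Schedule of Activities (Protocol 1.3) marks AE recording at Visit 3 as well, separately from MAEs and SAEs. That does not agree with Protocol 8.5.1, but it is a discrepancy about collection and does not bear on the choice of a 30-day window.

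**Conclusion.** No change to the plan follows. SAP 6.1.3 makes a legitimate choice for the primary AE window and states it. What remains is a missing detail: the window of the tier and overall AE summaries. Analysts can fill it sensibly by summarising all AEs collected, as those sections already read. No data are lost, all AEs are listed, and late MAEs and SAEs have their own table.

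The size supports this. The difference between the two windows is about 0.5 to 1.8 points, and about 0.4 to 2.0 participants per group of 148 have neither a late MAE nor a late SAE. Both figures rest on assumed AE proportions of 10% to 20%, even visit timing, the two hazard shapes, full enrolment split evenly and, for the second, a 25% to 50% share with a late MAE or SAE. Across visit timings the difference runs from 0 to 3.85 points, the upper end requiring every Visit 2 on the last permitted day. Even that is well inside sampling error in a descriptive study with no hypothesis test.

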### 6.1.4. MAEs and SAEs Through 6 Months After Vaccination

- Analysis population: Safety ([Section 4](#)).
- Analysis time points: Day 1 through Month 6 after vaccination.
- Analysis methodology: Descriptive summary statistics.
- Supporting objective: Primary safety objective.
- For each group, the number of participants with AEs within 6 months (n), proportion, and associated 2-sided exact 95% CI will be presented for any MAEs and SAEs, each SOC, and each PT within each SOC, by vaccine group.

